3. SUMMARY OF STUDY PLAN

Study Design

Eligible individuals must be at least 21 years of age or older, with a low-grade, clinically localized prostate cancer. Individuals must have had a prostate biopsy within 13 months of study entry. Use of 5 α reductase inhibitors is prohibited during the study, and for six months prior to the baseline study visit.

Thirty participants will be accrued to this study. Participants will be stratified by tumor volume (≤ 2 positive cores and $\leq 10\%$ of any biopsy core volume is adenocarcinoma vs. >2 positive cores or $> 10\%$ of any biopsy core volume is adenocarcinoma). We expect an enrollment duration of 12-18 months. Participants will be randomized, in a 1:1 ratio, to one of two treatment groups:

PFE (as POMx™) 1000mg (i.e., one (1) 1000mg capsule) taken each morning, by mouth, for 52 weeks ± 1 week

Placebo (0mg PFE) one (1) capsule taken each morning, by mouth, for 52 weeks ± 1 week

Following the baseline visit, participants will return for evaluation at 13, 26, 39 and 52 weeks. Scheduled evaluations/procedures are as follows:

- **Baseline Visit:** Eligibility, safety labs and total PSA (to be processed at the PO's clinical lab). Medical history, physical exam, review of concomitant medications and baseline symptom assessment. Blood and urine collection for research purposes (to be batch shipped when a participant completes the study for analysis by the CP lab at UWI. Analysis will include total serum PSA for doubling time, serum testosterone, plasma pharmacokinetics, plasma biomarkers, and urine pharmacokinetics). Review of the pre-study biopsy clinical pathology report for verification of the presence of adenocarcinoma, confirmation that the Gleason grade meets study eligibility criteria, and for stratification by tumor volume. Participants will be stratified by tumor volume and randomized to one of the two treatment groups.
- **Week 13 and 39 Visits:** Safety labs and total PSA (to be processed at the PO's clinical lab), review of adverse events and concomitant medications, pill count and compliance review, blood and urine collection for research purposes (batch shipped to the CP lab at UWI for analysis of total serum PSA, plasma pharmacokinetics and biomarkers and urine pharmacokinetics).
- **Week 26 Visit:** Physician visit, safety labs and total PSA (to be processed at the PO's clinical lab), review of adverse events and concomitant medications, pill count and compliance review, blood and urine collection for research purposes (batch shipped to the CP lab at UWI for analysis of total serum PSA, plasma pharmacokinetics and biomarkers and urine pharmacokinetics).

- **Week 52 ± 1W or End-of-study visit:** Physician visit, safety labs and total PSA (to be processed at the PO's clinical lab), review of adverse events and concomitant medications, pill count and compliance review, blood and urine collection for research purposes (batch shipped to the CP lab at UWI for analysis of total serum PSA, plasma pharmacokinetics and biomarkers and urine pharmacokinetics).
 - Prostate Biopsy – participants will undergo a “standard-of-care” prostate biopsy (8-12 cores from apex, mid-gland, base). Should a study participant elect to undergo surgery, prior to completion of the 12 month study period, (secondary to progression or participant preference) efforts will be made to obtain prostate tissue from the prostatectomy for histology and molecular studies (PSA, IGF-1, IGFBP-3, apoptosis (CASPASE 3), Ki-67, IGF-1R, 8OHdG and androgen receptor), and to obtain all other end of study assessments.
 - If the participant discontinues study therapy and a prostatectomy is not planned, if at all possible, perform a biopsy prior to the participant initiating non-study therapy and obtain all other end of study assessments.
 - Plasma and urine ellagic acid, dimethyl ellagic acid, urolithin A, urolithin B and their corresponding glucuronides will be evaluated by LCMSMS as previously described by Seeram (Seeram et al, 2006). LCMSMS is a standard analytical technique with improved sensitivity over HPLC.

4. PARTICIPANT SELECTION

4.1 Inclusion Criteria

- 4.1.1 Participants must have had a standard-of-care biopsy within 13 months of the baseline study visit and must have been diagnosed with low-grade, clinically localized prostate cancer (Gleason Score $\leq 3+3$ with a PSA at baseline $<10\text{ng/ml}$ in participants <70 years of age, OR Gleason Score $\leq 3+4$ with a PSA at baseline $\leq 15\text{ng/ml}$ in participants ≥ 70 years of age). Eligible participants will be those men who are able and willing to undergo AS with PSA monitoring and a scheduled biopsy performed at the end of the study.
- 4.1.2 No concurrent treatment (hormonal, radiation or systemic chemotherapy) for prostate cancer during study enrollment is planned (unless participants demonstrate clinical evidence of prostate cancer progression such as symptoms, physical exam findings, a rapidly increasing PSA, or radiologic findings that confirm disease progression).
- 4.1.3 Age ≥ 21 years. Because no dosing or adverse event data are currently available on the use of POMx™ in participants <21 years of age, children are excluded from this study.
- 4.1.4 ECOG performance status ≤ 1 (see Appendix A)
- 4.1.5 Participants must have normal organ and marrow function as defined below:

- 4.1.5.1 Hematologic:
WBC $\geq 3000/\text{mm}^3$;
platelets $\geq 100,000/\text{mm}^3$,
hemoglobin ≥ 10 g/dL
- 4.1.5.2 Hepatic:
Total bilirubin ≤ 1.5 x upper limit of institutional normal,
alkaline phosphatase ≤ 1.5 x upper limit of institutional normal,
AST ≤ 1.5 x upper limit of institutional normal,
ALT ≤ 1.5 x upper limit of institutional normal
- 4.1.5.3 Renal:
Serum creatinine within 1.5 x upper limit of institutional normal
- 4.1.5.4 Electrolytes:
Sodium 135-144 mmol/L (inclusive),
Potassium 3.2-4.8 mmol/L (inclusive),
- 4.1.6 The effects of PFE on the developing human fetus at the recommended therapeutic dose are unknown. For this reason, participants will be required to use a medically approved method of birth control or abstinence if their sexual partner is of childbearing potential.
- 4.1.7 Participants must be willing to forego foods, beverages and supplements containing pomegranate for the duration of the study.
- 4.1.8 Ability to understand, and the willingness to sign, a written informed consent document.

4.2 Exclusion Criteria

- 4.2.1 Any prior surgery to the prostate within 30 days of baseline procedures. NOTE: Biopsies are not considered surgeries.
- 4.2.2 Evidence of other cancer(s) (excluding non-melanoma skin cancer) within last 5 years.
- 4.2.3 Prior pelvic radiation for any reason.
- 4.2.4 Participants cannot be taking 5- α -reductase inhibitors while on study or within 6 months of the baseline study visit.
- 4.2.5 Participants may not be taking carbamazepine (tegretol).
- 4.2.6 Participants may not be receiving any other investigational agents.
- 4.2.7 History of allergic reactions attributed to compounds of similar chemical or biologic composition to PFE.

- 4.2.8 Uncontrolled intercurrent illness including, but not limited to, ongoing or active infection, or psychiatric illness/social situations that would limit compliance with study requirements.
- 4.2.9 Any significant cardiac event(s) within the 12 months prior to registration, such as episodes(s) of symptomatic congestive heart failure; myocardial infarction; unstable angina pectoris or persistent, stable angina pectoris; or cardiac arrhythmia requiring medication.

4.3 Inclusion of Women and Minorities

Women will not be enrolled in this study of prostate cancer. Members of all races and ethnic groups are eligible for this trial. According to NCI Surveillance Epidemiology and End Results (SEER) 2002 data, the incidence of new prostate cancer diagnosed in the USA during 2002 was distributed ethnically as follows: 5% Hispanic and 94% non-Hispanic; and racially as: 83% white, 12% black, 5% other races. According to SEER the median age at diagnosis for cancer of the prostate is 69 years of age. Approximately 0.0% of those diagnosed are under age 20; 0.0% between 20 and 34; 0.5% between 35 and 44; 8.0% between 45 and 54; 26.1% between 55 and 64; 37.5% between 65 and 74; 23.2% between 75 and 84; and 4.7% 85+ years of age. We expect the age and race distribution to be similar on our study.

The planned distribution of subjects for our study will be men \geq 21 years old of all racial/ethnic groups with low grade, early stage prostate cancer, who have chosen AS of their prostate cancer. Prostate cancer is only relevant to male gender thus women will be excluded.

It is scientifically and ethically imperative that clinical research into diseases that affect large populations are performed in a way that the knowledge gained can be generalized to the larger population. This means the research subjects need to reflect the population at large. This is especially important in cancer research where data have observed differences in incidence and outcome based upon race/ethnicity or socioeconomic status. Prostate cancer incidence in the United States varies with race/ethnicity, an example being African-Americans, who are at increased risk compared to other races. Therefore, it is critical that adequate representation is achieved.

Because the University of Wisconsin has limited racial/ethnic diversity in our clinical catchment area, we developed a GU prevention group not only focusing on the research expertise of the Urologists involved, but also on achieving more diversity of race/ethnicity and economic status. The University of Wisconsin Carbone Cancer Center serves a multi-county area in southern Wisconsin and northern Illinois that is rural with <5% prostate cancer cases occurring in underserved racial/ethnic populations. In addition, advertisements and contacts with Urologic practices in Milwaukee County, which has a greater proportion of African-Americans, will be targeted. The University of Rochester has a prostate cancer population that is more reflective of the general population with 12-15% of patients being African-American. The University of Minnesota/Minneapolis Veterans Hospital serves both a rural and urban population with approximately 10% of prostate cancer patients being African-

American. The University of Alabama-Birmingham (UAB) serves predominantly an urban population with approximately 35% of prostate cancer patients being African-American. UAB was one of the initial clinical research sites to incorporate community-involvement in their recruitment efforts toward minority populations. In addition to working with community churches that are predominately African-American, they also worked with local barbershops to encourage participation in prostate cancer screening and prevention studies. Urology of San Antonio is a community-based Urologic practice in the city of San Antonio, TX that has been an integral participant in our GU prevention studies. Their participation insures adequate representation of Latino men in our study. Approximately 35% of their prostate cancer patients are Hispanic and 5% are African-American. The Lahey clinic provides another more urban community setting to facilitate diverse representation of subjects. Their distribution according to race/ethnicity is approximately: 83% white, 4% black, 1% Hispanic, <1% Asian, <1% other, and 11% unknown.

4.4 Recruitment and Retention Plan

Subjects will be recruited from Urology clinics at the participating organizations. Study personnel at each PO will be contacted by a patient's Urologist or will contact the PO's Urologists for permission to approach potential subjects they consider appropriate for the study. Local IRB-approved posters or recruitment materials may be placed in Urology clinics identifying the study and directing the potential subjects to notify clinic staff they may be interested in the study. Study personnel would contact the potential subject. When potential subjects are interested, the study will be described by their Urologist and/or study personnel in a private setting. In addition to the study being described, an Informed Consent will be given to the potential subject and family to read and consider. All potential subjects will undergo an informed consent process and will be required to read and sign an Informed Consent form documenting their acknowledgement and desire to be a human research participant.

After the consent form is signed, all procedures and examinations will be done at one visit, including research blood and urine sample collection. Subjects found to be screen failures will not be randomized and the research samples will be destroyed on-site.

Study brochures, posters, protocol fast fact sheets, pocket cards, and other recruitment materials will be developed at the CLO (Consortium Lead Organization – the University of Wisconsin) and made available to the POs for use or modification. The CLO will coordinate with the POs to develop comprehensive site-specific recruitment plans.

5. AGENT ADMINISTRATION

5.1 Dose Regimen and Dose Groups

There will be two treatment groups for this trial. Participants will be randomized in a 1:1 ratio to one of the two groups. The treatment groups are as follows:

Group 1: PFE as POMx™ 1000mg, i.e., one (1) 1000mg capsule, taken each morning, by mouth, for 52 weeks ± 1 week.

Group 2: Placebo, one (1) capsule, taken each morning, by mouth, for 52 weeks ± 1 week.

5.2 Study Drug Administration

Drug will be dispensed by investigational pharmacists or appropriate study staff at the participating organizations and self-administered by the participants. Participants will take one capsule per day, in the morning, by mouth. Study medication may be taken with or without food.

To ensure that study subjects have access to study drug in case of delayed study visit, they will be dispensed four (4) bottles (120 capsules) of study agent at each visit. Tear-off labels will be utilized for unblinding purposes.

5.3 Run-in Procedures

There is no run in phase for this study.

5.4 Contraindications

During study participation, participants may not consume any additional pomegranate, either through dietary sources or through nutritional supplementation.

5.5 Concomitant Medications

As stated in section 5.4, study participants may not consume any additional PFE either in beverage form or as a dietary supplement.

The use of 5- α -reductase inhibitors (finasteride, dutasteride) is not allowed while on study or within 6 months prior to the baseline study visit. These agents have been shown to affect serum PSA values and may or may not affect prostate cancer biology.

All medications (prescription and over-the-counter), vitamin and mineral supplements, and/or herbs taken by the participant will be documented on the Concomitant Medications Worksheet and will include: date reported, medication name, start and stop date, dosing regimen, and indication. Medications taken for a procedure (e.g., biopsy) should also be included.

5.6 Dose Modification

The study drug dose modification schema is as follows:

IF	THEN
The participant experiences a grade 2 adverse event that is possibly, probably, or definitely related to study drug	Stop study drug temporarily for up to 4 weeks.
The adverse event resolves to \leq grade 1 within 4 weeks:	Re-start study drug at 50% dose reduction (1 capsule should be administered every other day).
If the adverse event does not resolve to \leq grade 1 within 4 weeks:	Stop study drug permanently. Continue to follow participant per the schedule of events in Section 7.1, if participant is willing.
If the participant experiences a grade 2 event after initial dose reduction, and the adverse event is possibly, probably or definitely related to study drug:	Stop study drug permanently and follow until the adverse event is resolved to \leq grade 1. Continue to follow participant per the schedule of events in Section 7.1, if participant is willing.
In the event a subject had study drug stopped while on the 50% dose reduction, for a grade 2 adverse event that is NOT possibly, probably or definitely related to study drug	Stop study drug temporarily for up to 4 weeks. If the adverse event resolves to \leq grade 1 within 4 weeks, re-start study therapy at the 50% dose reduction level. If the adverse event does NOT resolve to \leq grade 1 within 4 weeks, permanently discontinue study drug. Continue to follow participant per the schedule of events in Section 7.1, if participant is willing.
A grade 3 or 4 adverse event occurs, regardless of relationship to study drug	Stop study drug and call protocol chair to determine if and when drug should be re-started.

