7. CLINICAL EVALUATIONS AND PROCEDURES

7.1 Schedule of Events

Evaluation/Procedure	Baseline	Randomization	Week 13 (+/- 1 week) ¹	Week 26 (+/- 1 week) ¹	Week 39 (+/- 1 week) ¹	Week 52 ± 1 Week (or end of study therapy) ¹
Informed consent	x					
Registration	x					
Eligibility Criteria Review	x					
Medical History	x					
Physical Exam	x			x		x
Vital Signs (Temp, BP, Pulse, Respirations) and Weight	x		x	x	x	x
Height	x					
ECOG Performance Status	x					
Assess baseline symptoms	x					
Eligibility/Safety Labs ²	x		x	x	x	x
Total PSA ³	x		x	x	x	x
Randomization		x				
Dispense study medication and diary		x ⁴	x	x	x	
Pill count and drug calendar review			x	x	x	x
Review concomitant medications	x		x	x	x	x
Assess adverse events						x
Prostate Biopsy	x ⁵					x ⁶
The samples listed below will be collected locally, and shipped to UWI for analysis:						
Collect one 3ml red top ⁷	x		x	x	x	x
Collect a second 3ml red top ⁷	x			x		x
Two 10ml green tops ⁷	x		x	x	x	x
Urine collection ⁷	x		x	x	x	x
IHC analysis of normal and abnormal prostate tissue biomarkers (PSA, IGF-1, IGFBP-3, apoptosis [CASPASE 3], Ki-67, IGF-IR, 8OHdG and androgen receptor)	x ⁸					x ⁹

¹The participant must delay his dose of study medication until after blood and urine has been collected, as PK levels need to be assessed approximately 24 hours following the last dose of study medication.

²The following lab tests are to be performed: WBC, Hemoglobin, Platelets, Alkaline Phosphatase, ALT, AST, Total Bilirubin, Serum Creatinine, Sodium, Potassium, Chloride, and Bicarbonate. Eligibility labs must be done \leq 30 days of randomization.

³This total serum PSA will be performed at the PO's clinical lab, and used for clinical purposes.

⁴If the participant is unwilling or unable to return to clinic to pick up study medication, it may be sent overnight by a courier service such as UPS or Fed-Ex.

⁵ The baseline biopsy must have occurred within 13 months prior to the baseline study visit.

⁶The end of study biopsy performed during week 52 ± 1 week or when participant discontinues study therapy. Participant must take study drug the morning of the biopsy after research blood and urine collection but prior to the biopsy.

⁷These blood and urine samples will be used to determine study objectives (PK and biomarker results) as described in §1.2. See §10.2 for collection and processing instructions.

⁸Tissue will be from a biopsy performed within 13 months of study entry

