7.2.12 Drug Dispensing and Compliance Instructions

Participants will be instructed on the importance of compliance with the study agent dosing instructions (section 5) Participants will be provided with a pill diary and instructed to document daily the date and time they take their dose of study agent, indicate the reason for any missed doses, document any lost capsules of study agent, list any side effects or symptoms noticed, list any new concomitant medications taken and indication for that medication and note any additional information they feel is relevant. The participant will be instructed to initial each day's entry.

All bottles of study agent dispensed to the participant must be accounted for by the PO. Participants will be instructed to return all bottles of study agent (empty, full, or partially full) and all unused capsules of study agent that were previously dispensed to them at their next study visit.

No study agent bottles should be discarded by the participant or by study staff. Returned bottles of study agent will be maintained at the site for review by a study monitor and return to the drug repository (MRIGlobal).

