13.2 Sample Size/Accrual Rate

The sample size for each group is based on comparing the change in IGF-1 levels between the PFE and placebo arms. According to ELISA assay analysis, this primary endpoint can be considered a continuous random variable. The sample size justification is thus based on a two-tailed two-sample t-test of the difference between the two groups at a significance level of 0.05. In order to detect an effect size of 1.10, i.e. the difference in the mean change between the two groups of 1.10 standard deviations, with power 0.80, or an effect size of 1.17 with power 0.85, the trial requires an effective sample size of 14 per group. Assuming a random dropout of up to 5%, 15 subjects per group will be enrolled for a total of 30 subjects for this exploratory study.

There will be six organizations participating in the study. With each PO randomizing one participant per month, a conservative estimate, the study will enroll the target accrual goal of 30 subjects within 6 months. Considering the usual delay due to start-up, it may take up to 18 months. Each randomized participant will be treated with study medication for one year. We will allow for a study duration of two-three years.

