13.5 Secondary Objectives

For the secondary objectives, we will compare compliance and toxicities for a once daily oral administration over a 12-month period of time between the PFE and placebo groups. We will compare the modulation of the following biomarkers with response to PFE versus placebo: plasma biomarkers, including IGF-1/IGFBP-3 ratio, total serum PSA and normal and abnormal prostate tissue biomarkers, including PSA, IGFBP-3, apoptosis (CASPASE 3), Ki-67, IGF-1R, 8OHdG and androgen receptor. We will also compare PFE constituents/metabolites for evidence of accumulation (trough levels): ellagic acid, dimethyl ellagic acid, dimethyl ellagic acid glucuronide (DMEAG), urolithin A, urolithin A glucuronide, urolithin B and urolithin B glucuronide between the treatment groups. Serum testosterone levels will also be measured.

For secondary objectives, all measurements and changes in measurements of interest will be summarized by treatment arm (and, if applicable, by visit) with appropriate descriptive statistics. Compliance, in terms of the number of pills missed, will be summarized by treatment arm with descriptive statistics, and tested for imbalance using Wilcoxon rank-sum test. Patient toxicity throughout the study will be summarized in several ways; the presence or absence of any toxicities, worst CTCAE grade, and strongest investigator-defined relationship will all be examined and characterized by treatment arm, and analyzed appropriately (Wilcoxon rank-sum for ordinal data, Fisher's exact test for dichotomous data, and log rank test for time to event data). We will examine the differences between the groups for the change from baseline for serum biomarkers, tissue biomarkers, and PFE constituents/metabolites with the appropriate tests; for dichotomous data we will use Fisher's exact test, for ordinal data we will use Wilcoxon rank-sum test, and for continuous data, and a two-sample t-test with normalizing transformation if necessary or Wilcoxon rank-sum test.

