13.6 Reporting and Exclusions

As the nature of this study is exploratory, intent-to-treat should not be used as a principal analysis criterion. Nevertheless, no subjects will be excluded from the analysis and reporting, except for obvious random dropouts and for those who never took the protocol treatment.

Compliance with the protocol treatment will be measured in the form of pill counts, but the information will not be used for the primary analysis. There will be no imputation of missing data for both the primary and the secondary endpoints.

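### Section 13.5 compares PFE metabolites between arms as trough levels, but samples taken during holds, on every-other-day dosing or after permanent stopping are not 24-hour troughs and bias the PFE arm downward

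*Combined protocol and SAP*

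**What the plan says.** - **Intended timing.** Section 7.1 footnote 1 has participants delay the visit-day capsule because "PK levels need to be assessed approximately 24 hours following the last dose of study medication". Sections 7.3.1 and 7.4 repeat the instruction. Research blood and urine are collected at weeks 13, 26, 39 and 52.
- **Departures from daily dosing.** Section 5.6 allows a hold of up to 4 weeks. If the event resolves, the instruction is "Re-start study drug at 50% dose reduction (1 capsule should be administered every other day". If it does not: "Stop study drug permanently. Continue to follow participant per the schedule of events in Section 7.1, if participant is willing".
- **Analysis.** Section 13.5 states: "We will also compare PFE constituents/metabolites for evidence of accumulation (trough levels". It sets no condition on current regimen or on hours since the last dose.
- **Exclusions.** Under Section 13.6, "no subjects will be excluded from the analysis and reporting, except for obvious random dropouts and for those who never took the protocol treatment".
- **Compliance.** Section 5.7.1 sets 80% for evaluability and does not count holds as non-compliance. Section 7.3.1.5 divides capsules taken by capsules prescribed for the period.
- **Data available.** Under Section 7.2.12 participants are "instructed to document daily the date and time they take their dose of study agent". Section 10.2 has blood and urine tubes labelled with time and date of collection.

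**The concern.** Delaying the visit-day capsule gives a 24-hour sample only if the man took a capsule the day before. Section 5.6 creates three situations in which he may not have done so: a hold, every-other-day dosing, and permanent stopping. An ordinary missed dose on the previous day, within the 80% allowance, has the same effect.

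Objective 1.2.5 asks whether the constituents accumulate, judged from trough levels. A sample taken 48 hours after a dose, or weeks after the last one, does not measure that. In the PFE arm such values lie below the daily-dosing trough. In the placebo arm there is no drug to lose. The error therefore runs one way, towards a smaller difference between arms.

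**Working it through.** **1. The plan's own figure.** Section 13.2 sizes the trial for IGF-1 with a "two-tailed two-sample t-test of the difference between the two groups at a significance level of 0.05". The first target reads: "In order to detect an effect size of 1.10" (in SD units), at power 0.80; the second is 1.17 at power 0.85. Noncentral-t power at 14 per group is 0.800 and 0.846. Dropout: 14 / (1 − 0.05) = 14.7, rounded up to 15. The sizing reproduces and does not depend on this point. No power is stated for the metabolite comparison.

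**2. Does any rule remove these samples?** The 80% rule does not do so reliably. Holds do not count against compliance, and a man on every-other-day dosing who takes every prescribed capsule scores 100%. Section 13.6 then names only random dropouts and never-treated men as exclusions. Nothing in Section 13 uses the diary times.

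**3. Every-other-day dosing.** The documents give no half-life, so 12 to 48 h is assumed, in a one-compartment model at steady state. Let e = 2^(−24/half-life). Relative to the daily-dosing trough, e/(1 − e), the every-other-day value is:
- at 48 h after the dose: [e²/(1 − e²)] / [e/(1 − e)] = e/(1 + e)
- at 24 h after the dose: [e/(1 − e²)] / [e/(1 − e)] = 1/(1 + e)

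| Assumed half-life | e | 48 h sample | 24 h sample |
|---|---|---|---|
| 12 h | 0.25 | 20% | 80% |
| 24 h | 0.50 | 33% | 67% |
| 48 h | 0.71 | 41% | 59% |

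Which column applies depends only on whether the visit falls on a dosing day.

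**4. The planned between-arm comparison.** Assumptions: 14 men per arm, log-scale SD 0.5, off-drug men given placebo-like values, two-sided Wilcoxon rank-sum test at 0.05, power by simulation. A true ratio of 2 is ln 2 / 0.5 = 1.39 SD. With m off-drug men left in, the average ratio in the PFE arm is [2(14 − m) + m]/14.

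| m | Average ratio | Power, left in | Power, set aside |
|---|---|---|---|
| 0 | 2.00 | 0.92 | – |
| 1 | 27/14 = 1.93 | 0.86 | 0.91 |
| 2 | 26/14 = 1.86 | 0.80 | 0.90 |
| 3 | 25/14 = 1.79 | 0.71 | 0.88 |

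At a true ratio of 3 (ln 3 / 0.5 = 2.20 SD), power with three men left in is still about 0.97 to 0.98. At a ratio of 5 it stays at about 1.0.

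**5. How many men?** The documents give no rate of dose modification. For 15 PFE men and an assumed rate q, the expected number is 15q and the chance of at least one is 1 − (1 − q)^15:
- 2%: 0.3 men; 0.26
- 5%: 0.75 men; 0.54
- 10%: 1.5 men; 0.79
- 20%: 3.0 men; 0.97

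**The case against.** Four arguments limit the point.

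- **Few men may be affected.** Section 6.2 reports gastrointestinal effects in under 2% at 1000 mg, and permanent stopping for a grade 2 event needs non-resolution or recurrence. This largely stands: at 2%, fewer than one PFE man is expected. It is not the whole rate, because grade 3–4 events of any cause also stop drug under Section 5.6, and missed previous-day doses add to it.
- **Section 7.4 may prevent late off-drug samples.** It puts the final visit at week 52 or end of therapy, whichever is first. That conflicts with the continued schedule in Section 5.6, and the documents do not settle it. Even under Section 7.4 the sample need not be a trough, since one route to permanent stopping follows a hold of up to 4 weeks.
- **A large difference survives.** This stands, as step 4 shows.
- **Half-life is undocumented.** This also stands. Section 2.2.2 reports rapid clearance of ellagic acid but urinary urolithins for 48 hours, so the seven analytes will differ and no single figure in step 3 fits all of them.

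A reader might infer that the later visits are where accumulation would show, so that stops building up over the year would hide a rise from week 13 to week 52. The documents do not support this. Section 13.5 specifies change from baseline compared between arms, not a within-arm contrast of week 13 with week 52. Nor would such a rise be expected: week 13 is 91 days in, and even a one-week half-life gives 13 half-lives, or 1 − 2^(−13) = 99.99% of steady state. Nor does any documented rate support assuming two or three PFE men off drug.

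**Conclusion.** The gap is real and the direction of bias is clear. As written, Section 13.5 puts values that are not 24-hour troughs into a comparison of trough levels, and Sections 5.6 and 13.6 keep them there. PFE-arm levels are lowered at whichever visit those samples occur.

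The size is modest. At a true ratio of 2, the loss of power from leaving men in rather than setting them aside is about 0.05 for one man (0.91 − 0.86), 0.10 for two (0.90 − 0.80) and 0.17 for three (0.88 − 0.71). At a ratio of 3 or more it is small. These figures rest on assumed variability, numbers of men affected and placebo-like off-drug values; the every-other-day percentages rest on an assumed half-life. The point concerns secondary objective 1.2.5 only. Following men after they stop drug is not itself a fault, and the IGF-1 primary analysis is unaffected. The change is still worth making, because the stated analysis dilutes the quantity it sets out to measure and the data to prevent this are already collected.

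**What to change.** In Section 13.5, before unblinding:

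1. Derive hours since last dose for every research sample from diary dose times (Section 7.2.12) and sample collection times (Section 10.2).
2. Base the trough and accumulation comparison on samples taken about 24 hours after a dose, for example 20 to 28 hours, during uninterrupted daily dosing.
3. List all other samples separately by hours since last dose and current regimen.

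Separately, reconcile Section 5.6 (scheduled visits continue after a permanent stop) with Section 7.4 (final visit at end of therapy if that comes first), so that it is clear which samples a man who stops will contribute.

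The cost is one derived variable and a short addition to Section 13.5. A few samples leave the trough analysis, which then describes men on daily dosing rather than all randomized men; the text should say so. No change to dosing or to the IGF-1 analysis is needed.
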